5.2 Treatment Exposure

Treatment Duration

Duration of treatment as total number of weeks on trabectedin and/or PLD will be calculated as follows:

$$\left(\frac{\text{lastdosedate} - \text{firstdosedate} + 21\text{days}}{7} \right)$$

Treatment duration should not, however, go beyond date of death or the start date of a subsequent anti-cancer treatment.

Cycle

Cycle duration will be calculated as the time from the administration of trabectedin and/or PLD for the given cycle to the day before the administration of the subsequent cycle. The last cycle duration for a patient will be set to 21 days (but no later than death or start of subsequent anti-cancer treatment).

Dose Intensity

Weekly dose intensity (mg/week) is calculated as:

Cumulative dose received / Total number of weeks on drug (treatment duration)

Relative Weekly Dose Intensity

Relative weekly dose intensity = (Reported weekly dose intensity / Expected weekly dose intensity) x 100

Derived Body Surface Area (BSA)

BSA will be calculated by the following Mosteller formula to:

$$\text{BSA (m}^2\text{)} = \sqrt{(\text{height(cm)} \times \text{weight(kg)}) / 3600}$$

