5.1.1 Duration of Treatment

There is no predefined limit as to the number of cycles of treatment with trabectedin. Treatment may continue as long as the treating physician feels there is benefit, even in the presence of apparent disease progression.

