6.2 Observation Period

The Observation Period will begin with the first trabectedin + PLD dose administered after the signing of the ICF and will continue for up to a total of 12 months after that or until trabectedin treatment discontinuation, patient discontinuation for any reason or patient's death. PLD discontinuation is not a reason for Observation Period discontinuation. There are no predefined limits to the number of cycles administered. Trabectedin + PLD treatment can continue at the treating clinician's discretion.

Methods and timing of the imaging procedures will be determined by the treating clinician.

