6.2.2 Subsequent Visits during Observation Period

Subsequent visits will occur at the treating clinician's typical schedule. On each subsequent visit during the Observation Period, the following data, if available, will be collected:

- 1. Complete physical examination (including weight, height, and BSA).
- 2. Evaluation of performance status using ECOG/WHO PS score.
- 3. Safety assessment (all AEs including ADRs and SADRs).
- 4. Imaging procedures and results of imaging response evaluations will be collected, if they are available, during each cycle of the Observation Period of the study. Symptomatic response will also be collected.
- 5. Laboratory tests will be collected when available and based on the treating clinician's usual practice procedures. When available, those laboratory tests associated with ADRs and SADRs will be collected.
- 6. Data on trabectedin + PLD treatment administration.

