3. STUDY OVERVIEW

3.1 Study Design

This is a non-interventional, prospective, multicenter study including at least 300 patients from approximately 70 sites from Germany, Italy, Spain, France, and Belgium, with platinum-sensitive relapsed ovarian cancer for whom trabectedin + PLD is administered according to standard local clinical practice following approved SmPC indication and dose. There is no involvement with any treatment decisions for the patients included in the study.

To be enrolled in this study, the patients must meet all inclusion criteria and have none of the exclusion criteria. The reason(s) for not enrolling a patient in the study (patient declined, no reply, patient not fulfilling the selection criteria) are recorded in a patient qualification log at each site. This enables subsequent assessment of potential selection bias necessary for quality assurance of the data collected.

The study will begin with the enrollment of the first patient. The individual patient study duration will be up to 13 months (12-month Observation Period + 1-month Follow-up Period). Patients treated during the entire observation period will have a visit at month 12 and a follow up visit 1 month after. Patients ending treatment before the end of the 12 months observation period will, in addition to the 1 month after follow up visit, have an additional visit at month 12.

Trabectedin is administered every 3 weeks as a 3-hour infusion at a dose of 1.1 mg/m², immediately after PLD at 30 mg/m². There is no predefined limit as to the number of cycles of treatment with trabectedin. Treatment may continue as long as the treating physician feels there is benefit, even in the presence of apparent progression of disease.

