9. STATISTICAL METHODS OF ANALYSIS

9.1 General Principles

All analysis will be based on the FAS and will be presented overall and by previous antiangiogenic usage (yes/no).

Appropriate descriptive statistics will be produced for each parameter. For continuous data the mean, standard deviation, median, minimum and maximum will be presented. For categorical data, the frequency and percentage in each category will be presented. The data will be analyzed using the normal approximation and its 95% CI. However, in analyses where sample size is considered to be too low, the exact binomial estimator and its 95% CI will be calculated. Time-to-event endpoints (PFS and OS) and their fixed-time estimations will be analyzed using the Kaplan-Meier (KM) method.

Any p-values presented will be descriptive in nature and the significance level selected will be 5%.

Statistical analyses will be conducted using SAS version 9.4 or later for Windows, and/or any other applicable software suitable for the planned statistical analyses.

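### SAP 5.2 takes the last dose recorded by 12 months after Index as the end of treatment, so mean and maximum duration, cycles and cumulative dose are too low if patients are still on treatment at that point

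*SAP*

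**What the plan says.** **The window.** Under Protocol 6.2 the Observation Period starts with the first dose after consent (the Index date) and "will continue for up to a total of 12 months after that or until trabectedin treatment discontinuation", withdrawal or death. Earlier cycles are collected retrospectively where available (Protocol 6.2.1).

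**Treatment length.** Protocol 5.1.1: "There is no predefined limit as to the number of cycles of treatment with trabectedin". SAP 3.1 adds: "Treatment may continue as long as the treating physician feels there is benefit, even in the presence of apparent progression of disease". It also provides for patients who fill the window: "Patients treated during the entire observation period will have a visit at month 12 and a follow up visit 1 month after".

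**What is collected.** Protocol 6.2.2 lists, for Observation Period visits, "Data on trabectedin + PLD treatment administration". The follow-up list in Protocol 6.3 has no dosing item and asks only for later anti-cancer treatment other than trabectedin. It does mention an evaluation of treatment duration, and it asks for the reason for stopping where applicable.

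**How it is analysed.** SAP 5.2: "Duration of treatment as total number of weeks on trabectedin and/or PLD will be calculated as follows", followed by (last dose − first dose + 21 days)/7. The result is capped at death or at the start of another anti-cancer treatment, and every patient's last cycle is set to 21 days. SAP 9.1 and 9.4.4 give duration, cycles and cumulative dose plain descriptive statistics. Kaplan-Meier is named elsewhere only: "Time-to-event endpoints (PFS and OS) and their fixed-time estimations will be analyzed using the Kaplan-Meier (KM) method".

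**The concern.** A patient still receiving trabectedin 12 months after Index has no observed end of treatment. The SAP formula nevertheless closes that patient's exposure at the last recorded dose plus 21 days, exactly as for a patient who stopped. SAP 5.2 has no ongoing status and no censoring rule, and SAP 9.4.4 has no footnote on it. SAP 9.5.4 points the same way, since it equates the end of the observation period with the last dose plus 30 days.

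Treatment duration, number of cycles and exposure are stated secondary objectives, overall and by prior antiangiogenic use. A reader of the report would take a mean of so many weeks, or a maximum of so many cycles, as a description of how long patients were treated. In part it would describe how long they were watched. The cut-off, counted from first dose, also differs between patients, because Index can be cycle 2 or later.

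**Working it through.** **Plan's own figure.** There is none to reproduce. The documents state no expected duration, cycle count or cumulative dose. The sample size of at least 300 has no inputs behind it and is used below only to turn shares into counts.

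**Inputs from the documents.** 12-month window from Index; at least one cycle before inclusion (Protocol 4.3.1); 3-week cycles; month = 30.4375 days (SAP 5.3).

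**Assumed inputs.** Median time on treatment of 4, 6, 7.4 or 9.7 months. The first is near the SAP's 6-cycle split (6 × 21 / 30.4375 = 4.1 months). The last two are the phase III median PFS values in Protocol 1.1.3.1 (partially platinum-sensitive and all platinum-sensitive). They would apply only if patients were treated to progression.

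**Step 1: what can be recorded.** With Index at cycle 2, the cut-off from first dose is 12 + 21/30.4375 = 12.69 months.
- Maximum cycles: 1 + 1 + floor(365.25/21) = 19.
- Maximum duration by the SAP formula: (21 + 365.25 + 21)/7 = 58.2 weeks.
- With six cycles before Index: 24 cycles and 73.2 weeks.

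The reported maximum therefore reflects the window and the consent date once anyone is treated past the cut-off.

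**Step 2: the mean, exponential times.** With λ = ln 2/median and cut-off c, the share still on treatment is S(c) = exp(−λc), and the recorded mean is (1 − S(c))/λ against a true mean of 1/λ. Example, median 6: λ = 0.1155, S(12.69) = 0.231, and 8.66 × (1 − 0.231) = 6.66. The constant 21 days is left out of both means.

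| Assumed median (months) | Still on treatment | Of 300 | True mean | Recorded mean | Change |
|---|---|---|---|---|---|
| 4 | 11.1% | 33 | 5.77 | 5.13 | −11.1% |
| 6 | 23.1% | 69 | 8.66 | 6.66 | −23.1% |
| 7.4 | 30.5% | 91 | 10.68 | 7.42 | −30.5% |
| 9.7 | 40.4% | 121 | 13.99 | 8.34 | −40.4% |

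**Step 3: another shape, in whole cycles.** Simulation of 3-week cycles among patients who reach cycle 2, with Index at cycle 2; mean cycles, recorded against true:

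| Median | Exponential | Weibull, shape 1.5 |
|---|---|---|
| 4 | 8.84 vs 9.85 (−10.3%) | 7.45 vs 7.51 (−0.8%) |
| 6 | 10.94 vs 14.02 (−21.9%) | 10.17 vs 10.78 (−5.7%) |
| 7.4 | 12.00 vs 17.01 (−29.5%) | 11.66 vs 13.11 (−11.1%) |
| 9.7 | 13.22 vs 21.80 (−39.4%) | 13.42 vs 16.93 (−20.7%) |

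At constant dose, mean cumulative dose falls in the same proportion. The SD also falls, because cutting every time at c brings values closer together.

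**Step 4: what does not move.**
- Median: the share ongoing stays below one half in every row. Simulated median cycles were identical with and without the cut-off (7, 10, 12, 16 exponential; 7, 9, 11, 15 Weibull).
- Split at 6 cycles: on schedule, the sixth cycle starts on day 5 × 21 = 105 after first dose, against a cut-off at about day 386.
- Dose intensity: dose and weeks are cut together. At constant dosing it is 1.1/3 = 0.367 mg/m² per week either way.

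**The case against.** The strongest reply is that this is a labelling matter of unknown and possibly trivial size. Treatment completed, toxicity and refusal are all listed stopping reasons, so treatment to progression is an upper anchor and not an expectation. With a 4-month median and a stopping hazard that rises over time, the loss is under 1%. This stands, and it limits what can be said about size.

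The documents also cover part of the gap. Protocol 10.4 calls for censoring-aware methods for time-to-event data without limiting them to PFS and OS. The stopping reason is collected only where applicable, so a blank can identify an ongoing patient. Table shells are held separately and could contain an ongoing row. SAP 9.2 reports cycles and time before consent. The follow-up visit's evaluation of treatment duration might move the cut-off by up to a month. None of this supplies a rule in SAP 5.2, whose formula has caps for death and later therapy but none for ongoing treatment.

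A reader might infer more than the text supports:
- *All exposure endpoints are too low.* The planned median, the 6-cycle split and dose intensity are not.
- *The mean is low by exactly the share ongoing.* That holds only for exponential times.
- *The figures are too low for everyone who starts the regimen.* Entry needs an earlier cycle and a further on-study dose, which removes early stoppers and raises mean exposure. With exponential times, a 4-month median and Index after two cycles, the recorded mean is 6.43 months. The true mean is 7.15 for enrolled patients (−10%) but 5.77 for all starters (+11%). The downward direction is certain only for enrolled patients.
- *Differences by prior antiangiogenic use are always narrowed.* That needs comparable windows in both groups, and the window varies with consent date. No formal comparison is planned.
- *End-of-treatment ECOG will be filled in for ongoing patients.* SAP 9.4.4 does not say so; it is silent.

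**Conclusion.** The point holds in limited form. For enrolled patients still on treatment at Index + 12 months, SAP 5.2 takes the end of recording as the end of treatment. If there are such patients, the mean, SD and maximum of duration, and the mean and maximum of cycles and cumulative dose, are biased low. The size cannot be fixed from the documents. About −1% to −40% on the mean is the range over the assumed medians and the two shapes, with Index at cycle 2. The median would be affected only if about half of the patients were still on treatment at the cut-off, and even a 9.7-month median gives about 40%. PFS is untouched. This is a cheap and worthwhile correction to descriptive secondary endpoints and does not threaten the study's main result.

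**What to change.** In SAP 5.2 and 9.4.4:

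1. Report the number and percentage still on treatment at the end of observation, overall and by prior antiangiogenic use.
2. Present time on treatment by Kaplan-Meier, with discontinuation as the event and ongoing patients censored. Use the same time scale as the SAP duration formula, and state how the added 21 days are treated for events and for censored patients.
3. Let patients enter the risk set at Index, because nobody could be observed to stop before it. Otherwise state plainly that results apply to enrolled patients only. A curve from Day 1 without one of these would overstate the share of all starters still on treatment at early time points.
4. Label mean and maximum duration, cycles and cumulative dose as recorded up to the end of the Observation Period.
5. Label the ECOG value of ongoing patients as last observed, not end of treatment.

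Dose dates and stopping reasons are already collected. The cost is SAP wording and one more table, and the plain mean duration is no longer the headline figure. The Kaplan-Meier median will probably match the plain one. The gain lies in the proportions on treatment over time and in totals that are not misread.

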4.3.1 Selection Criteria

Patients must comply with all of the following criteria in order to be enrolled into the study:

- Patients must be aged 18 years or older.
- Patients must have platinum-sensitive relapsed ovarian cancer, defined as disease relapse that occurs 6 months or more after completion of last platinum-containing therapy.
- Treatment indication according to local label SmPC and reimbursement for trabectedin and PLD treatment.
- Patients must have received a minimum of 1 cycle of trabectedin + PLD before their inclusion in the study.
- Patients must have signed an informed consent document indicating that they understand the
 purpose and procedures required for the study and are willing to participate in the study.

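### Capping treatment duration at death or next therapy also shortens the dose-intensity denominator, so weekly and relative dose intensity are inflated when either event falls within 21 days of the last dose

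*SAP*

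**What the plan says.** SAP 5.2 (Treatment Exposure) builds the measure in steps.

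- Duration: "Duration of treatment as total number of weeks on trabectedin and/or PLD will be calculated as follows", followed by (last dose date − first dose date + 21 days)/7.
- Cap: "Treatment duration should not, however, go beyond date of death or the start date of a subsequent anti-cancer treatment".
- Last cycle, with the same cap: "The last cycle duration for a patient will be set to 21 days (but no later than death or start of subsequent anti-cancer treatment".
- Weekly dose intensity: "Cumulative dose received / Total number of weeks on drug (treatment duration". The words in brackets identify the capped duration as the divisor, and no uncapped alternative is given.
- RDI: "Relative weekly dose intensity = (Reported weekly dose intensity / Expected weekly dose intensity) x 100". The expected term is not defined anywhere, and no upper limit on RDI is set.

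SAP 9.4.4 and Protocol 10.4.4 plan weekly and relative dose intensity for both drugs. SAP 4 lists treatment exposure as a secondary endpoint. SAP 9.1 says "For continuous data the mean, standard deviation, median, minimum and maximum will be presented", overall and by prior antiangiogenic use.

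**The concern.** Each dose is meant to cover a 21-day interval, which is why the duration formula adds 21 days after the last dose. When the cap applies, the last dose is still counted whole but the interval it was meant to cover is cut short. Two patients with identical doses on identical dates then get different dose intensities, only because one of them died or changed therapy soon after the last infusion. The measure picks up outcome where it should describe drug delivery.

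The distortion always runs upward, and it falls on patients whose treatment ended badly or abruptly. A reader of the exposure table could take a high maximum or a wide SD as over-delivery. If the timing of death or switching differs between patients with and without prior antiangiogenic treatment, part of any difference in mean intensity between those groups would be artefact.

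**Working it through.** The documents give no dose-intensity figure to reproduce, so the SAP 5.2 definitions are applied directly.

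**Inputs**
- Duration formula, cap, intensity and RDI definitions: SAP 5.2.
- Planned interval of 21 days: SAP 3.1, "Trabectedin is administered every 3 weeks as a 3-hour infusion".
- Assumption: expected weekly intensity = planned dose / 3 weeks. The SAP does not say so. Dose in mg, and hence body surface area, cancels.
- Assumption: n full planned doses given on schedule, with death or new therapy k days after the last dose (k ≤ 21).

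**Formula.** Capped duration in days is 21(n − 1) + k. Hence

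RDI = 100 × 21n / [21(n − 1) + k].

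**Check.** At k = 21 the cap does nothing and RDI = 100 × 21n/21n = 100% for every n.

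**Results**

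| Full doses (n) | Cap at day 7 | Cap at day 14 | Limit as k approaches 0 |
|---|---|---|---|
| 2 | 42/28 = 150% | 42/35 = 120% | 42/21 = 200% |
| 3 | 63/49 = 128.6% | 63/56 = 112.5% | 63/42 = 150% |
| 6 | 126/112 = 112.5% | 126/119 = 105.9% | 126/105 = 120% |

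Weekly intensity in mg/week is inflated by the same ratios. It has no expected term, so this holds however that term is defined.

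**Delayed cycles.** An affected value need not exceed 100%. Two full doses 28 days apart with the cap at day 7 give 42/35 = 120%, against 42/49 = 85.7% uncapped.

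**Day counting.** If the day of the event is also counted, the two-dose, day-7 case becomes 42/29 = 144.8%. The point is unchanged.

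**One-dose patients.** RDI = 2100/k %, that is 150% at day 14, 300% at day 7 and 700% at day 3. Such patients should be rare. Protocol 4.3.1 states "Patients must have received a minimum of 1 cycle of trabectedin + PLD before their inclusion in the study", and the Observation Period starts with the first dose after consent, which footnote 1 of Protocol Table 1 places at cycle 2 or later. They are not excluded, however. Protocol 6 allows consent from one day after the first administration, and the full analysis set in SAP 6.1 requires enrolment and one trabectedin administration, not an on-study dose.

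**Effect on summary statistics** (share affected assumed at 2–5%; the documents give no figure)
- Two-dose excess: 50 points at day 7 and 20 at day 14, average (50 + 20)/2 = 35.
- Shift in the mean: 0.02 × 35 = 0.7 to 0.05 × 35 = 1.75 points.
- SD: if all other patients were at exactly 100% and the affected ones at 150%, the artefact alone would give √(0.02 × 0.98 × 50²) = 7.0 points at 2% and √(0.05 × 0.95 × 50²) = 10.9 points at 5%.
- Maximum: one affected patient can set it.
- Median: little changed when at most 5% of values move.

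**After the change.** With (last − first + 21)/7 as denominator, on-schedule full dosing gives 100% for any n, whatever the date of death or new therapy.

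**The case against.** The best defence is that the SAP is consistent with itself. It applies one cap to treatment duration and to the last cycle, no stated figure is wrong, and time after death or after a switch is plainly not time on treatment. Dose intensity is also not read alone. Cycles started, dose per infusion, cumulative dose, cycle duration and dose modifications are tabulated beside it, so a careful reader could recognise a short-denominator outlier. The median is reported too. No primary or safety conclusion depends on RDI.

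Most of this stands, and it is why the point is minor. It justifies the cap as a description of duration, but not its use as the divisor of a dose that is counted in full.

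The undefined expected term gives a partial defence. If expected intensity were computed over the same capped weeks, the inflation would cancel in RDI. It would remain in mg/week, which is reported separately.

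A reader might infer three stronger things that the documents do not support.

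- *That 300% is a ceiling.* It is the one-dose, day-7 case. A single dose with an earlier event gives more, while two or more on-schedule doses cannot exceed 200%.
- *That early death as such is the cause.* The trigger is death or new therapy within 21 days of the last dose, at any point in treatment. An early death 22 days or more after the last dose has no effect.
- *That the mean rises by 1.6–4.0 points.* This needs one-dose patients to make up half of those affected: the average of 300, 150, 150 and 120 is 180, an 80-point excess, and 80 × 2–5% gives 1.6–4.0. The enrolment rules make one-dose patients too rare for that weight.

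**Conclusion.** The point holds as a minor defect of definition. SAP 5.2 divides a last dose counted in full by an interval cut at death or next therapy, which inflates mg/week intensity in every affected patient. RDI is inflated as well on the natural, but unstated, reading of expected intensity. The distortion is sizeable for a patient with few cycles and small after six. Its effect on the mean is small on the assumed 2–5% of patients, and it bears mainly on the SD and maximum. The true share affected cannot be judged from the documents. PFS, response, survival and safety analyses are untouched.

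**What to change.** In SAP 5.2:

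1. Use the uncapped (last dose date − first dose date + 21)/7 as the denominator of weekly and relative dose intensity.
2. State that expected weekly intensity is the planned dose per 3-week cycle divided by 3.
3. Keep the cap for the descriptive treatment-duration and cycle-duration summaries only.

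The cost is one or two SAP sentences and a matching line in the derivation code. It needs no new data, no design change and no change to patient management.
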